7.2.1. Multiple Myeloma

7.2.1.1. Endpoint / Variables

7.2.1.1.1. Overall Response Rate

Overall Response Rate (ORR), is defined as the percentage of responders (subjects with confirmed stringent complete response (sCR), complete response (CR), very good partial response (VGPR), and partial response (PR) as assessed according to 2011 International Myeloma Working Group (IMWG) criteria (Appendix 1 in the protocol)). Only the assessments from the start of treatment up to the earlier of disease progression or the start of new anti-cancer therapy will be considered. Only new systemic anti-cancer drugs taken are considered as anti-cancer therapy (radiotherapy and surgeries are not considered as systemic anti-cancer therapy for the purpose of this analysis). .

Subjects with only one assessment (therefore not confirmed), or assessments of Not Evaluable or missing response will be treated as non-responders; i.e. they will be included in the denominator when calculating the percentage.

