7.3.1.2. Summary Measure

7.3.1.2.1. Progression-Free Survival

PFS is defined as the interval of time between the date of first dose and the earlier of the date of first disease progression and the date of death due to any cause. Disease progression will be based on the assessments by the Investigator.

If there is no adequate baseline assessment, the subjects will be censored at their date of first dose. Subjects without any adequate post-baseline tumor assessments will be censored at the date of first dose.

Subjects who progressed or died after an extended period without adequate assessment will be censored at their date of last adequate assessment prior to progression or death even if subsequent information is available regarding progression or death. An adequate assessment is defined as an assessment where the Investigator determined response is sCR, CR, VGPR, PR, MR or SD. The date of response at that assessment will be used for censoring. As the assessment schedule may change through the course of the protocol, specific rules for identifying extended loss to follow-up or extended time without an adequate assessment are provided in Section 16.5.4.

For subjects who receive subsequent anti-cancer therapy the following rules will apply:

- If the start date of the anti-cancer therapy is partial (i.e. either missing the day but has the month and year available or missing both day and month), the imputation rules described in Section 16.7.2.1 will be applied. No imputation will be made for completely missing dates.
- If anti-cancer therapy is started without documented disease progression or death OR is started prior to documented disease progression or death, then PFS will be censored at the date of the last adequate assessment that is no later than the date of initiation of anti-cancer therapy (i.e. if an assessment occurs on the same day as the start of new anti-cancer therapy the assessment will be used - as it will be assumed the assessment occurred prior to the administration of new anti-cancer therapy). The date of response at the last adequate assessment will be used as the censoring value.
- If a subject has only a baseline visit or does not have an adequate assessment that is no later than the date of initiation of anti-cancer therapy, PFS will be censored at the date of first dose.

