33. Optional follow-up telephone interview to explore visual symptoms and changes in symptoms and related impacts following treatment discontinuation be performed at least 6 months following the End of Study Treatment visit. This interview would only be for those subjects who experienced corneal symptoms during treatment and consent to participate.
34. End of treatment visit should be performed within 30 days (+7 days) after the last dose or prior to the start of new anti-cancer treatment, whichever is earlier. In cases where more than 30 days (+7 days) have elapsed from the date of the subject's last dose due to dosing delays and a subsequent decision to take the subject off treatment, the end of study treatment visit should be scheduled as soon as possible to allow the final assessments to be performed at the earliest date.

35. Participants with corneal signs or symptoms at the end of study treatment visit should be monitored by ophthalmic exam once a month after the last study dose until deemed clinically stable by an eye care professional complete resolution or for 12 months (whichever comes first). Corneal exams to include BCVA and slit lamp examination (with special focus on cornea). Participants who have completed treatment or the 3 month follow up visit (end of study) will be re-consented for additional ophthalmology follow up.

Abbreviations:

ADA = Antibody Drug Antibody; ALP = alkaline phosphatase; BCVA = best corrected visual acuity; BNP = B-type natriuretic peptide; C1D1 = Cycle 1 Day 1, etc.; cfdNA = Circulating free DNA; CK = creatinine kinase; CRP = C-reactive protein; EM = extramedullary; EOI = End of Infusion; FLC = free light chain; PD = Pharmacodynamics; PK = Pharmacokinetics; QID = 4 times a day; SOI = start of infusion; SPEP = serum protein electrophoresis; UPEP = urine protein electrophoresis

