Concomitant Medications	
 • Partial dates for any concomitant medications recorded in the CRF will be imputed using the following convention: 
 ○ If the partial date is a start date, a '01' will be used for the day and 'Jan' will be used for the month ○ If the partial date is a stop date, a '28/29/30/31' will be used for the day (dependent on the month and year) and 'Dec' will be used for the month. • The recorded partial date will be displayed in listings.

Element	Reporting Detail
Anti-Cancer Therapy (Where applicable), Radiotherapy and Surgical Procedures for Time-to-Event Endpoint and Response	
 • Start dates for follow-up anti-cancer therapy, radiotherapy (where applicable), and surgical procedures (where applicable) will be temporarily imputed in order to define event and censoring rules for progression-free survival, response rate, time to progression, duration of response or time to response (i.e. start date for new anti-cancer therapy). The imputed dates will not be stored on the anti-cancer therapy, radiotherapy, or surgical procedure datasets. • If missing start day, month, and year, then no imputation for completely missing dates • If missing start day and month, then no imputation should be done • If missing start day, then do the following: • If partial date falls in the same month as the last dose of study treatment, then assign to earlier of (date of last dose of study treatment+1, last day of month). • If partial date falls in the same month as the subject's last assessment and the subject's last assessment is PD, then assign to earlier of (date of PD+1, last day of month). • If both rules above apply, then assign to latest of the 2 dates • Otherwise, impute missing day to the first of the month. • If missing end date, then no imputation should be done.

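### A progression after the last dose that is followed by a not-evaluable visit can be censored out of PFS, TTP and DOR, because the partial-date rule for new therapy looks only at the last assessment

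*SAP*

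**What the plan says.** SAP Section 16.7.2.1 sets out how a follow-up anti-cancer therapy start date is imputed for PFS, response rate, TTP, DOR and TTR. When only the day is missing, the rules run in this order:

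- Last-dose exception: "If partial date falls in the same month as the last dose of study treatment", the date becomes the earlier of last dose + 1 and month end.
- PD exception: if the date is in the month of the subject's last assessment, and the "last assessment is PD, then assign to earlier of (date of PD+1, last day of month").
- Tie-break: "If both rules above apply, then assign to latest of the 2 dates".
- Default: "Otherwise, impute missing day to the first of the month".

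The imputed date is then used in two ways. In Section 7.3.1.2.1 and Table 5, PFS is censored at the last adequate assessment on or before new therapy if therapy precedes documented progression. Table 6 does the same for TTP, and Section 7.3.1.2.3 gives DOR the TTP censoring rules. In Section 7.2.1.1.1, only assessments "up to the earlier of disease progression or the start of new anti-cancer therapy will be considered" for ORR.

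For dates that give only the year, Section 7.3.1.2.1 says that if the date is "missing both day and month), the imputation rules described in Section 16.7.2.1 will be applied". Section 16.7.2.1 says: "If missing start day and month, then no imputation should be done".

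**The concern.** The PD exception is evidently meant to keep a documented progression ahead of the new therapy that follows it. It does so only while PD is the last assessment on record. The term is not defined, and Section 7.2.1.1.2 handles NE as an assessment result. The Part 2 myeloma schedule (Section 16.2.3.1) lists no M-protein or free light chain test at the end-of-treatment visit, so an NE entry after a PD is plausible there.

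When that happens, the imputed therapy date can fall before the PD, and the subject is censored although progression was observed. Censoring of this kind is informative: it removes a subject from the risk set just before a known event, and so can bias PFS, TTP and DOR upward.

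**Working it through.** The plan gives no figure to reproduce, so the check traces the rules on hypothetical dates.

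**Inputs from the SAP.** The imputation rules are those of Section 16.7.2.1. An adequate assessment is sCR, CR, VGPR, PR, MR or SD, so neither NE nor PD qualifies (Section 7.3.1.2.1). PD on the same day as new therapy counts as an event (Table 5, note 3). Confirmation takes the lower of two consecutive assessments and ignores NE (Section 7.2.1.1.2).

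**Assumed dates.** First dose is 8 April 2017 and new therapy is recorded as June 2017 with the day missing. Study day = date − first dose + 1, so 20 May is 42 + 1 = 43, 22 May is 45, 10 June is 63 + 1 = 64 and 23 June is 76 + 1 = 77.

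| Case | Last dose | Assessments | Imputed therapy | PFS | Best confirmed response |
|---|---|---|---|---|---|
| 1 | 20 May | SD 29 Apr, SD 20 May, PD 10 Jun | 11 Jun | event, day 64 | SD |
| 2 | 20 May | as 1, then NE 19 Jun | 1 Jun | censored, day 43 | SD |
| 3 | 2 Jun | SD 29 Apr, SD 20 May, PD 23 Jun, NE 28 Jun | 3 Jun | censored, day 43 | SD |
| 4 | 10 Jun | SD 29 Apr, SD 20 May, PD 10 Jun, NE 19 Jun | 11 Jun | event, day 64 | SD |
| 5 | 20 May | PR 29 Apr, PR 20 May, PD 10 Jun, NE 19 Jun | 1 Jun | censored, day 43 | PR |
| 6 | 20 May | SD 29 Apr, PR 20 May, PR 10 Jun | 1 Jun | censored, day 43 | SD |
| 7 | 10 Jun | SD 29 Apr, PR 20 May, PR 10 Jun | 11 Jun | censored, day 64 | PR |
| 8 | 1 May | SD 29 Apr, PD 22 May, NE 5 Jun | 1 Jun | event, day 45 | PD |

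**Reading the table.**

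- Cases 1 and 2 differ only by a later NE visit, yet the progression is counted in one and lost in the other.
- Case 3 shows that a last dose earlier in the same month does not repair this: therapy goes to 3 June and the PD of 23 June is still lost.
- Cases 4 and 7 show what the last-dose exception does protect, namely assessments up to the last dose and the day after it.
- Case 5 loses the PFS event, and its DOR event of 10 June likewise becomes a censoring at 20 May. Responder status stays PR, so ORR does not change.
- Case 6 is the only path that lowers ORR. The confirming PR comes after the last dose, in the month of new therapy.
- Case 8 is unaffected, because the PD is in an earlier month than new therapy.

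**How far the last-dose exception reaches.** Taking each day of 2017 as the last dose, an assessment 21 days later falls in the same calendar month for about 31% of dates; 30 days later, about 2%; 37 days later, none. The gaps are assumptions. For most post-dose assessments, then, the last-dose exception does not apply in the month of the assessment. These shares do not say how often new therapy starts in that month.

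**With the PD exception keyed to the first documented PD.** Case 2 becomes an event on day 64 (therapy 11 June), case 3 an event on day 77 (therapy 24 June) and case 5 an event on day 64. Cases 1, 4, 7 and 8 do not change. Case 6 is restored to PR only if the rule is also extended to a confirming response; PFS censoring then moves from day 43 to day 64.

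**The case against.** The strongest reply is that the problem is an undefined term. Section 16.5.5 dates a response by the visit at which the investigator assessed disease. If disease is not assessed at the end-of-treatment visit, the PD remains last and is protected, as in case 1. Section 7.2.1.1.2 also ignores NE when pairing assessments. A programmer could therefore reach the intended result. That is a fair reading, but the literal wording does not require it, and the same section treats NE as an assessment result.

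It also stands that the affected window is narrow. The assessment must come after the last dose, new therapy must be recorded in the same month, and the day must be missing.

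Four stronger readings are tempting and are not supported:

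- That every date goes to the first of the month unless the last assessment is PD. The last-dose exception contradicts this (cases 4 and 7).
- That a lost PD also lowers ORR. It does not (cases 2 and 5).
- That the schedule rules out the imputed date. Footnote 34 of Section 16.2.3.1 does place the end-of-treatment visit "prior to the start of new anti-cancer treatment, whichever is earlier", but as something that should happen, and it allows for delayed visits. It also has no bearing on case 6, which includes no such visit.
- That therapy dated only by year is simply ignored in censoring. That is an inference; the SAP does not say so.

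On those year-only dates, one can argue that Section 7.3.1.2.1 merely points to Section 16.7.2.1, whose answer is to impute nothing. But Section 7.3.1.2.1 reserves no imputation for completely missing dates, so the two sections still read differently.

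**Conclusion.** The point holds for a PD after the last dose that is followed by an NE visit, with PD and new therapy in the same month and the therapy day missing. Such a subject is censored in PFS, TTP and DOR instead of counted as progressed. This rests on the NE visit counting as the last assessment, which the wording permits. ORR can fall only through an unconfirmed response as in case 6, where one subject is 1/40 = 2.5 points in the planned maximum of 40.

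The total effect cannot be sized, because the SAP does not say how many start dates lack the day. A reader might infer a percentage increase in median PFS from assumed event counts. That is not supported: the counts would be guesses, and scaling by lost events alone ignores the follow-up time that earlier censoring also removes.

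PFS, TTP and DOR are exploratory, ORR is secondary, and no hypothesis test is planned for the Part 2 myeloma cohort. The change should still be made: the rule can discard the progression it was written to protect. The conflict over year-only dates needs settling regardless of how many subjects it touches.

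**What to change.** In Section 16.7.2.1, replace the PD exception with: if the recorded month contains the subject's first documented PD, assign the earlier of PD + 1 and month end, whether or not a later NE visit exists. Keep the last-dose rule, and take the later date when both apply.

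Optionally, treat a confirming response after the last dose in that month in the same way. The downside is that an assessment made after therapy truly began could be counted, which may raise ORR. This part is a matter of judgement, and the main correction does not depend on it.

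Make Sections 7.3.1.2.1 and 16.7.2.1 agree on whether a date with only the year is imputed, and state how such subjects are censored.

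The cost is a few lines of SAP text and code, with no change to data collection.

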16.8. Appendix 8: Values of Potential Clinical Importance

16.8.1. Laboratory Parameters

Reference ranges for all laboratory parameters collected throughout the study are provided by the laboratory. A laboratory value that is outside the reference range is considered either high abnormal (value above the upper limit of the reference range) or low abnormal (value below the lower limit of the reference range). Note: a high abnormal or low abnormal laboratory value is not necessarily of clinical concern. The laboratory reference ranges will be provided on the listings of laboratory data. Clinical laboratory test results outside of the reference range will be flagged in the listings.

To identify laboratory values of potential clinical importance, National Cancer Institute Common Terminology Criteria for Adverse Events (NCI-CTCAE v4.0) will be used to assign grades to the relevant laboratory parameters. NCI-CTCAE v4.0 can be found at <http://ctep.cancer.gov/reporting/ctc.html>.

For laboratory data which are not listed in the NCI CTCAE v4.0, a summary of values outside the normal range will be provided.

16.8.2. ECG Parameters and vital signs

For ECG and vital signs, the most updated IDSL standard up to the RAP effective date will be followed

16.9. Appendix 9: Population Pharmacokinetic (PopPK) Analyses

16.9.1. Population Pharmacokinetic (PopPK) Dataset Specification

Any deviations between the dataset specification and the final dataset will be documented in the population pharmacokinetic analysis report.

General Description:

1. The type of variables should be either NUM or DATE/TIME unless specified otherwise
2. The dataset is sorted by ID, RTFDD, ANALN, ASCENDING EVID unless specified otherwise
3. The data items (columns) in the analysis-ready data file will be in the same order as follows.
4. Exclude observations with DTYPE=IMPUTE
5. Include PKFL=Y (applicable to all datasets)
6. Same rules are applied for other baseline covariates. Baseline rules are as follows:
 - Use baseline value as defined by Stats in the lab test datasets;
 - If not defined by Stats, set to measurement nearest to, but prior to, time of first dose
 - Only in cases where Day 1 measurement is not available, but screening measurement is, the screening values will be used.
7. 3 significant figures for all values.

Column Header	Data Item	Codes	Derivation/Comments	Source data set
C	Line number/exclusion identifier	Row Number STM DRM PFD	Set to line/row number unless one or more of the following conditions are met, then set to code: 
 • STM = If a PK sample was taken but the date and/or time of the sample is missing and cannot be derived • DRM= PK samples for which dosing records are missing • PFD=PK samples with CONC reported as NA/NR/NQ/BQL/missing at pre-dose in CYCLE =1 	derived
STUDY	Study ID		1 = BMA117159	adpc
SUBJID	Subject identifier from source data		SUBJID = SUBJID	adsl
ID	NONMEM subject identifier		Sequential subject identifier across studies after data is sorted by SUBJID. Starting with P	derived

Column Header	Data Item	Codes	Derivation/Comments	Source data set
AMT	Amount of GSK2857916 given (in mg)		AMT = ALTDOSE, where PARAMCD=ALTDOSE only on the dosing line. For all other lines use "."	adex
INFD	Infusion Duration (day)		(AENDTM-ASTDTM)/60/60/24 This value will only be used on the dosing line. For all other lines use "."	adex
INFH	Infusion Duration (h)		(AENDTM-ASTDTM)/60/60 This value will only be used on the dosing line. For all other lines use "."	adex
RATED	Rate of infusion (mg/day)		RATED = AMT/INFD; where INFD is the infusion duration and is computed from start and stop time of infusion (in days) This value will only be used on the dosing line. For all other lines use "."	derived
RATEH	Rate of infusion (mg/h)		RATEH = AMT/INFH; where INFH is the infusion duration and is computed from start and stop time of infusion (in h) This value will only be used on the dosing line. For all other lines use "."	derived
RTFDD	Relative time from start of first infusion on study (day)		RTFDH=((ADTM-ASTDTM)/60/60/24)	adpc, adex
RTFDH	Relative time from start of first infusion on study (h)		RTFDD=((ADTM-ASTDTM)/60/60);	adpc, adex
RTLDD	Relative time from start of the most recent dose on study (day)		RTLDD = RTLDD/24	derived
RTLDDH	Relative time from start of the most recent dose on study (h)		AWNLRD = RTLDDH	adpc
NOMTLDD	Planned nominal time relative to start of most recent infusion (day)		NOMTLDDH/24	adpc
NOMTLDDH	Planned nominal time relative to start of most recent infusion (h)		Derive from PCTPT when (PCTPT = 'PRE-DOSE'), NOMTLDDH=0; when (PCTPT='DOSE'), NOMTLDDH =0; when (PCTPT = "30M POST START OF INFUSION (SOI)"), NOMTLDDH =0.5; when (PCTPT = "END OF INFUSION (EOI)"), NOMTLDDH =1; when (PCTPT = "1 HOUR POST-EOI"), NOMTLDDH =2; when (PCTPT = "3 HOURS POST-EOI"), NOMTLDDH =4; when (PCTPT = "8 HOURS POST-EOI"), NOMTLDDH =9; when (PCTPT = "24 HOURS POST-EOI"), NOMTLDDH =25; when (PCTPT = "7 DAYS POST-EOI"), NOMTLDDH =168; when (PCTPT = "14 DAYS POST-EOI"), NOMTLDDH	adpc

Column Header	Data Item	Codes	Derivation/Comments	Source data set
			=336; when (PCTPT ="END OF STUDY"), NOMTLDH =10000; otherwise NOMTLDH =.;	
CTIME	Clock time sample was obtained	Clock time (24 h) '00:00'	TIMEPART (EVENT) Format TIME5.	all dataset
DATE	Date of event (MM/DD/YYYY)		DATEPART (EVENT) Format DATE9.	all dataset
ANALN	Analyte	1= ADC(antibody-drug conjugate) 2= TOTALMAB(total antibody including complex) 3= MMAF(cys-mcMMAF)	This value will be used on all lines except for dosing record line where missing "." will be used. EXCLUDE MAB PARAMCD in (P1RES, P5RES, P7RES), assign ANALN =3, 1, 2 respectively	adpc
DV	Plasma concentration (ng/mL) of GSK2857916 (antibody-drug conjugate), total antibody (including complex) and cys-mcMMAF		If AVALC=NA/NR/NQ/BQL/missing, set DV= "." Else DV=AVAL When PARAMCD=P1RES, then DV=AVAL/1000 [Convert cys-mcMMAF from pg/mL to ng/mL precision (3 significant figures).For example, 0.111 pg/mL = 0.000111 ng/mL]	adpc
DNDV	Dose-normalized plasma concentration[(ng/mL)/(mg/kg)] of GSK2857916 (antibody-drug conjugate), total antibody (including complex) and cys-mcMMAF		DNDV = DV (ng/mL)/AVAL; where AVAL=adex.PARAMCD=ADOSE (mg/kg) For DV = ".", set DNDV = "."	adpc, adex
DVNM	Plasma concentration (nM) of GSK2857916 (antibody-drug conjugate), total antibody (including complex) and cys-mcMMAF		For ANALN = 1, DVNM = DV(ng/mL)/152.1 For ANALN = 2, DVNM = DV(ng/mL)/152.1 For ANALN = 3, DVNM = DV(ng/mL)/1.045 For DV = ".", set DVNM = "."	adpc
DNDVNM	Dose-normalized plasma concentration[(nM)/(mg/kg)] of GSK2857916 (antibody-drug conjugate), total antibody (including		DNDVNM = DVNM (nM)/ AVAL; where AVAL=adex.PARAMCD=ADOSE (mg/kg) For DVNM = ".", set DNDVNM = "."	adpc

Column Header	Data Item	Codes	Derivation/Comments	Source data set
	complex) and cys-mcMMAF			
LNDV	Natural logarithm of the plasma concentration of GSK2857916 (ng/mL) (antibody-drug conjugate), total antibody (including complex) and cys-mcMMAF		
 • If DV = "." then LNDV = "." • Else LNDV = loge(DV) 	adpc
LNDNDV	Natural logarithm of dose-normalized plasma concentration[(ng/mL)/(mg/kg)] of GSK2857916 (antibody-drug conjugate), total antibody (including complex) and cys-mcMMAF		If DNDV = "." then LNDNDV = "." Else LNDNDV = loge(DNDV)	adpc
LNDVNM	Natural logarithm of plasma concentration (nM) of GSK2857916 (antibody-drug conjugate), total antibody (including complex) and cys-mcMMAF		If DVNM = "." then LNDVNM = "." Else LNDVNM = loge(DVNM)	adpc
LNDNDVNM	Natural logarithm of dose-normalized plasma concentration[(nM)/(mg/kg)] of GSK2857916 (antibody-drug conjugate), total antibody (including complex) and cys-mcMMAF		If DNDVNM = "." then LNDNDVNM = "." Else LNDNDVNM = loge(DNDVNM)	adpc
DV2	Plasma concentration (ng/mL) of GSK2857916 (antibody-drug conjugate), total antibody (including complex) and cys-mcMMAF		If adpc.AVALC=NA/NR/missing, set DV2= "." If AVALC=NQ/BQL, set DV2 = "LLOQ/2" When PARAMCD=P1RES, then DV2=AVAL/1000; [Convert cys-mcMMAF from pg/mL to ng/mL precision (3 significant figures). For example, 0.111 pg/mL= 0.000111 ng/mL]	adpc
DNDV2	Dose-normalized plasma concentration[(ng/m		DNDV2 = DV2(ng/mL)/ AVAL; where AVAL=adex.PARAMCD=ADOSE (mg/kg)	adpc, adex

Column Header	Data Item	Codes	Derivation/Comments	Source data set
	L)/(mg/kg)] of GSK2857916 (antibody-drug conjugate), total antibody (including complex) and cys-mcMMAF		For DV2 = ".", set DNDV2 = "."	
DVNM2	Plasma concentration (nM) of GSK2857916 (antibody-drug conjugate), total antibody (including complex) and cys-mcMMAF		For ANALN = 1, DVNM2 = DV2(ng/mL)/152.1 For ANALN = 2, DVNM2 = DV2(ng/mL)/152.1 For ANALN = 3, DVNM2 = DV2(ng/mL)/1.045 For DV2 = ".", set DVNM2 = "."	adpc
DNDVN M2	Dose-normalized plasma concentration[(nM)/(mg/kg)] of GSK2857916 (antibody-drug conjugate), total antibody (including complex) and cys-mcMMAF		DNDVNM2 = DVNM2 (nM)/ADOSE (mg/kg) For DVNM2 = ".", set DNDVNM2 = "."	adpc
LNDV2	Natural logarithm of the plasma concentration of GSK2857916 (ng/mL) (antibody-drug conjugate), total antibody (including complex) and cys-mcMMAF		
 • If DV2 = "." then LNDV2 = "." • Else LNDV2 = loge(DV2) 	adpc
LNDNDV 2	Natural logarithm of dose-normalized plasma concentration[(ng/mL)/(mg/kg)] of GSK2857916 (antibody-drug conjugate), total antibody (including complex) and cys-mcMMAF		If DNDV2 = "." then LNDNDV2 = "." Else LNDNDV2 = loge(DNDV2)	adpc

Column Header	Data Item	Codes	Derivation/Comments	Source data set
LNDVNM2	Natural logarithm of plasma concentration (nM) of GSK2857916 (antibody-drug conjugate), total antibody (including complex) and cys-mcMMAF		If DVNM2 = "." then LNDVNM2 = "." Else LNDVNM2 = loge(DVNM2)	adpc
LNDNDVNM2	Natural logarithm of dose-normalized plasma concentration[(nM)/(mg/kg)] of GSK2857916 (antibody-drug conjugate), total antibody (including complex) and cys-mcMMAF		If DNDVNM2 = "." then LNDNDVNM2 = "." Else LNDNDVNM2 = loge(DNDVNM2)	adpc
BQL	Flag for BQL concentration	0 or 1	Set to 1 if adpc.AVALC= NQ/BQL; Else set to 0	adpc
MDV	Missing dependent variable flag.	0 or 1	1 for DV = "." and dosing line. 0 otherwise	adpc
MDV2	Missing dependent variable flag 2	0 or 1	1 for DV2= "." and dosing line. 0 otherwise	adpc
EVID	Flag indicating whether it is dosing admin info or drug concentration data.	0 or 1	1 on dosing line Set to 0 for all other lines	adex, adpc
OCC	Cycle number	>0	1 = Cycle 1, 2 = Cycle 2, 3 = Cycle 3 ,4 = Cycle 4,5 = Cycle 5,... etc EOT=999 Derive from AVISIT	adpc
IDOSE	GSK2857916 initial cycle dose (mg/kg)	>0	IDOSE=adex.TRT01A; strip off units	adex
ADOSE	GSK2857916 actual cycle dose (mg/kg)	>0	ADOSE= AVAL; where AVAL=adex.PARAMCD=ADOSE	adex
CMT	Compartment	>0	1 = Central Compartment for antibody-drug conjugate (Plasma concentration of antibody-drug conjugate ANALN=1) 3 = Central Compartment for total antibody (including complex) (Plasma concentration (DV) of total antibody for ANALN=2) 5 = Central Compartment for cys-mcMMAF (Plasma concentration(DV) of cys-mcMMAF for ANALN=3) On Dosing line CMT= 1	

Column Header	Data Item	Codes	Derivation/Comments	Source data set
AGE	Age (years)		
 Use value as defined by Stats; If not defined by Stats, AGE = date of first dose – date of birth If date of birth is missing, AGE = -99 	adsl
GENDE R	Gender	0 or 1	Male = 1 Female = 0 
 If sex is missing, GENDER = -99 	adsl
BWT	Baseline Weight (kg)		Baseline rules: 
 Use baseline value as defined by Stats in the lab test datasets; If not defined by Stats, set to weight measurement nearest to, but prior to, time of first dose Only in cases where Day 1 weight is not available, but screening weight is, the screening values will be used. Fill in BWT in all rows for each subject Same rules are applied for other baseline covariates	adsl
HT	Height (cm)		Height at baseline in cm Fill in HT in all rows for each subject	adsl
LNWT	Ln transformed weight (kg)		$LNWT = \log_e(BWT)$ Fill in LNWT in all rows for each subject	adsl
LWT	Lean Weight (kg)		Male: $0.32810 \cdot BWT(kg) + 0.33929 \cdot HT(cm) - 29.5336$ Female: $0.29569 \cdot BWT(kg) + 0.41813 \cdot HT(cm) - 43.2933$ Ref: Hume, 1966 Fill in LWT in all rows for each subject	adsl
LNLWT	Ln transformed lean Weight (kg)		$LNLWT = \log_e(LWT)$ Fill in LNLWT in all rows for each subject	adsl
BBSA	Baseline Body Surface Area (m ²)		Baseline BSA (m ²) $BBSA = 0.024265 \cdot HT(cm)^{0.3964} \cdot BWT(kg)^{0.5378}$ Fill in BBSA in all rows for each subject	adsl
BBMI	Baseline Body Mass Index (kg/m ²)		$BBMI = BWT(kg)/(HT(cm)/100)^2$ Assign BBMI = -99 if negative values would be derived for any of BBMI Fill in BBMI in all rows for each subject	adsl
BFFM	Baseline fat-free mass (kg)		
 If Male, BFFM = $(9270 \cdot BWT(kg))/(6680 + (216 \cdot BBMI(kg/m^2)))$ If Female, BFFM = $(9270 \cdot BWT(kg))/(8780 + (244 \cdot BBMI(kg/m^2)))$ Assign FFM = -99 if negative values are derived for any of BMI, BSA, FFM or IBW. Fill in BFFM in all rows for each subject	adsl
CANCER	Cancer type	0 or 1	0=Multiple Myeloma, 1=BCMA positive Lymphomas If TRT01AN = 12, then CANCER=1, else CANCER=0 Fill in CANCER in all rows for each subject	all datasets
BSBCMA	sBCMA level at baseline (ng/mL)		Baseline value is pre-dose on Cycle 1 Day 1. For PARAMCD = SBCMAG, get the values from AVAL column. When AVAL is missing: 
 and AVALC = ALQ: set to LBULOQ and AVALC = BLQ: set to LBLLOQ/2 	adbiomrk PARAMCD = SBCMAG when ABLFL=Y.

Column Header	Data Item	Codes	Derivation/Comments	Source data set
			
 and AVALC = missing: set to -99 Fill in the BSBCMA in all rows for each subject	
SBCMA	sBCMA level (ng/mL)		For PARAMCD = SBCMAG, get the values from AVAL column. SBCMA is propagated forward from the most recent measurement for all observations up to the next sBCMA measurement (LOCF). When AVAL is missing: 
 and AVALC = ALQ: set to LBULOQ and AVALC = BLQ: set to LBLLOQ/2 and AVALC = missing: propagate prior SBCMA value forward until the next measured SBCMA Please capture the values corresponding to the PK time points.	adbiomrk PARAMCD = SBCMA
SBCMAGC	Complex BCMA (ng/mL)		For PARAMCD = SBCMAGC, get the values from AVAL column. SBCMAGC is propagated forward from the most recent measurement for all observations up to the SBCMAGC measurement (LOCF). When AVAL is missing: 
 and AVALC = ALQ: set to LBULOQ and AVALC = BLQ: set to LBLLOQ/2 and AVALC = missing: propagate prior SBCMAGC value forward until the next measured SBCMAGC Please capture the values corresponding to the PK time points.	adbiomrk PARAMCD = SBCMAGC
BCRCL	Baseline Creatinine Clearance (mL/min/1.73 m ²)		$eGFR = 175 \times (Scr)^{-1.154} \times (Age)^{-0.203} \times (0.742 \text{ if female}) \times (1.212 \text{ if African American})$ Scr = AVAL; AVAL=adlab.PARAMCD =LB1404 and ABLFL=Y Convert units (µmol/L) to (mg/dL) using the following formula: To convert µmol/L to mg/dL, multiply by 0.0113. Age is expressed in years. Fill in the BCRCL in all rows for each subject Assign-99 if missing	adlab; PARAMCD=L B1404
CRCL	Creatinine Clearance (mL/min/1.73 m ²)		$eGFR = 175 \times (Scr)^{-1.154} \times (Age)^{-0.203} \times (0.742 \text{ if female}) \times (1.212 \text{ if African American})$ Scr = AVAL; AVAL=adlab.PARAMCD = PARAMCD=LB1404. Convert units (µmol/L) to (mg/dL) using the following formula: To convert µmol/L to mg/dL, multiply by 0.0113. Age is expressed in years.If AGE is changing during the course of treatment, then use baseline AGE. CRCL is propagated forward from the most recent measurement for all observations up to the next CRCL measurement (LOCF). Please capture the values corresponding to the PK time points.	adlab
BALT	Baseline ALT (IU/L)		BALT = AVAL; AVAL=adlab.PARAMCD =LB1227 and ABLFL=Y Fill in BALT in all rows for each subject	adlab

Column Header	Data Item	Codes	Derivation/Comments	Source data set
BAST	Baseline AST (IU/L)		BAST = AVAL; AVAL=adlab.PARAMCD =LB1273 and ABLFL=Y Fill in BAST in all rows for each subject	adlab
BALB	Baseline Albumin (g/L)		BALB = AVAL; AVAL=adlab.PARAMCD =LB1216 and ABLFL=Y Fill in BALB in all rows for each subject	adlab
BBILI	Baseline Total Bilirubin (mg/dL)		BALB = AVAL; AVAL=adlab.PARAMCD =LB1282 and ABLFL=Y Fill in BBILI in all rows for each subject	adlab
BIGG	Baseline serum IgG (g/L)		BIGG = AVAL; AVAL=adlab.PARAMCD =LB1566 and ABLFL=Y If a prior-to-first-dose-of- GSK2857916 lab test value was not available, set as -99 Fill in BIGG in all rows for each subject	adlab
IGG	Serum IgG (g/L)		BIGG = AVAL; AVAL=adlab.PARAMCD =LB1566 Missing values use -99. IGG is propagated forward from the most recent measurement for all observations up to the next IGG measurement (LOCF). Please capture the values corresponding to the PK time points.	adlab
MAXPRED	Maximum reduction in M-protein or FLC		Obtain AVAL for PARAMCD=MAXPRED. When AVAL is missing, MAXPRED = -999	adrs
RESPRATIO	Transform MAXRED to a ratio to baseline		RESPRATIO = $\max((100+\text{MAXPRED})/100, 0.001)$ 
 When MAXRED is missing, MAXPRED = -999 and RESPRATIO= -99 When MAXPRED is less than -100 e.g. -100.15, RESPRATIO = negative (It is negative but greater than -8.99), then update RESPRATIO = 0.001 When MAXPRED is equal to -100, RESPRATIO = 0, then update RESPRATIO = 0.001 	adrs
RACE	Subject race	1=White, or White/Caucasian, or White/Caucasian - European Heritage 2=Asian 3= Black or African American, or Black/African American, or Black - African American or African Heritage 4= American	If race is missing, set to other (use CRF/Stats coding for other) Fill in RACE in all rows for each subject	adsl

Column Header	Data Item	Codes	Derivation/Comments	Source data set
		Indian or Alaska Native, or Alaska Native or American Indian, or Alaska Native or American Indian from North/Central/South America 5= Native Hawaiian or Other Pacific Islander 6= Multi-racial: White Caucasian + Alaska Native or American Indian		
ETHN	Subject ethnicity	1 = Hispanic or Latino 2 = Non-Hispanic -99 = Missing	
 • Same coding as CRF/Stats • Fill in ETHN in all rows for each subject 	adsl
CNC	Country code	1 = Canada, 2 = UK 3 = US	Fill in CNC in all rows for each subject	adsl

Column Header	Data Item	Codes	Derivation/Comments	Source data set																												
IMMU	Immunogenicity Outcome by Collection Time	0 = negative 1 = positive	
  
 	PARAMCD	IMMU	
 
 	PARAMCD = AGBABDS	PARAMCD = AGBABDC		
   
 AVALC	NEGATIVE	MISSING	0	
 
 AVALC	POSITIVE	POSITIVE	1	
 
 AVALC	POSITIVE	NEGATIVE	0	
 
 AVALC	POSITIVE	MISSING	-99	
 
 AVALC	MISSING	ANY	-99	
  
 
IMMU may not have been assayed at all PK visits. For visits between IMMU visits, imputation rules are as follows:
 
 (1) When there is no change in IMMU between IMMU visits, all PK visits in between will be imputed with the same IMMU (2) When IMMU changes from 0 to 1, impute IMMU=1 from the first record after the record known to be IMMU=0 
When IMMU changes from 1 to 0, impute IMMU = 1 until the record known to be IMMU=0
		PARAMCD		IMMU		PARAMCD = AGBABDS	PARAMCD = AGBABDC		AVALC	NEGATIVE	MISSING	0	AVALC	POSITIVE	POSITIVE	1	AVALC	POSITIVE	NEGATIVE	0	AVALC	POSITIVE	MISSING	-99	AVALC	MISSING	ANY	-99	adis
	PARAMCD		IMMU																													
	PARAMCD = AGBABDS	PARAMCD = AGBABDC																														
AVALC	NEGATIVE	MISSING	0																													
AVALC	POSITIVE	POSITIVE	1																													
AVALC	POSITIVE	NEGATIVE	0																													
AVALC	POSITIVE	MISSING	-99																													
AVALC	MISSING	ANY	-99																													
IMM	Overall Immunogenicity Outcome 0=anti-GSK3174998 negative, 1=anti-GSK3174998 positive (at least one postdose)	0 = negative 1 = positive -99 = missing	
 • If IMMU = 1 at any observation for a subject, IMM = 1 • else if all IMMU = -99, IMM = -99 
Else IMM = 0
 
Fill in IMM in all rows for each subject
																													

